#### **10.7.1 Adverse Events**

The Medical Dictionary for Regulatory Activities (MedDRA) version 16.1 or later will be used to code all adverse events (AE) to a system organ class and a preferred term. All adverse event tables will be summarized by treatment group. Please refer to [section 6](#) for TEAE definition. Severity will be coded using CTCAE version 4.0 or later.

The subject incidence of AEs will be summarized for all treatment-emergent AEs, grade 3 and above AEs, serious AEs, treatment-related AEs, AEs leading to withdrawal of investigational product, fatal AEs, and AEs of interest (EOI). Subject incidence of EOIs will be summarized by SOC and PT according to the EOI search strategy categories defined by the EOI steering committee.

Subject incidence of all treatment-emergent AEs, grade 3 and above AEs, serious AEs, treatment-related AEs, AEs leading to withdrawal of investigational product, and fatal AEs will be tabulated by system organ class and preferred term in descending order of frequency.

Summaries of treatment-emergent and serious AEs occurring in at least 5% of the subjects by preferred term in any treatment arm may be provided in descending order of frequency.

When appropriate, subgroup analyses (if there is a medical rationale) will be presented by system organ class and preferred term in descending order of frequency. All races (if appropriate) with less than 5% of the total enrolled subjects will be pooled together for summary purposes.

### 10.7.2 Laboratory Test Results

Shift tables between the worst post-baseline and baseline values for selected laboratory parameters will be provided (based on the Common Terminology Criteria for Adverse Events ).

Graphs for the development of the following lab parameters will be provided:

- Immunoglobulin
- Thrombocytes (platelets)
- Liver parameters: alanine transaminase, aspartate transaminase, alkaline phosphatase, total bilirubin

### 10.7.3 Vital Signs

Notable values of systolic blood pressure, diastolic blood pressure and heart rate will be summarized at selected time points.

### 10.7.4 Antibody Formation

A table or listing summarizing the number and percentage of subjects with anti-drug antibodies to blinatumomab will be provided.

### 10.7.5 Exposure to Investigational Product

Descriptive statistics will be produced to describe the exposure to investigational product by dose cohort group and overall.

#### 10.7.5.1 Definitions of Variables Related to Study Drug Exposure

The duration of infusion in days

- within each cycle
- across cycles

will be calculated using the exact start and stop times of start of infusion, start and end of possible interruptions and stop of infusion. Any missing time will be imputed using the first start time of infusion of the respective cycle.

The relative treatment duration is defined as the duration of infusion received at each respective dose level relative to the planned duration of infusion of each dose level.

The absolute cumulative dose [ $\mu\text{g}$ ] is defined as:

$$\sum (\text{duration of infusion [days]for each dose received} \times \text{dose received}[\mu\text{g}])$$

The percent of the intended dose will be summarized. For patients who receive two or fewer cycles, this may be calculated using the absolute cumulative dose received

divided by the planned cumulative dose patients should have received through two cycles. Each cycle that was interrupted and later on restarted will be counted as two time 28 days of planned infusion, ie, if the first or second cycle is re-started, then the planned cumulative dose for the first two cycles will be based on three times 28 days. If a cycle was not re-started but continued after a shorter interruption, then the planned cumulative dose will be based on 56 days for the first two cycles.

For patients who received consolidation cycles the complete cumulative dose will be divided by the intended cumulative dose of all cycles that were started to compute the percent of the intended dose.

The number of cycles started is defined as the sum of the number of cycles. The number of re-started cycles will be analyzed separately.

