#### 3. **EXPERIMENTAL PLAN**

### 3.1 Study Design

This is an open-label combined two-part multi-center clinical study to evaluate the efficacy, safety, and tolerability of blinatumomab in adult and pediatric Japanese subjects with R/R B-precursor ALL.

The Phase 1b part will investigate the safety, efficacy, PK, and PD of blinatumomab to determine the MTD in both adult and pediatric subjects. In adult subjects, the Phase 2 part will assess the safety and efficacy of the recommended dose level of

Protocol Number: 20130265
Date: 20 March 2019

blinatumomab identified in the Phase 1b portion of the study in the adult study population.

The study design for both the Phase 1b and Phase 2 parts include:

- A 2-week screening and pre-phase period: The pre-phase period within the screening period is permitted for the administration of dexamethasone to reduce tumor burden and the incidence of tumor lysis syndrome.
- Induction phase: Up to two induction cycles of blinatumomab. A single cycle of blinatumomab is defined as 6 weeks in duration, which includes 4 weeks of continuous intravenous infusion (CIVI) of blinatumomab followed by a 2-week treatment-free interval.
- Consolidation phase: Subjects who achieve a bone marrow response (blasts ≤ 5%) within 2 induction cycles of treatment may continue to receive additional consolidation cycles of blinatumomab (up to a maximum of 5 total induction and consolidation cycles, or disease progression, intolerable adverse event or withdrawal of consent) under the same schedule as outlined in the induction treatment phase above.
- Safety follow-up visit: required 30 (± 3) days after last dose of blinatumomab.

Following the safety follow-up visit, subjects will be followed at 3, 6, 9, 12, 18, and 24 months (± 2 weeks) after treatment start for disease and survival status. Subjects will return to the clinic for assessments until relapse, with the following exceptions:

- Subjects who fail to achieve a bone marrow response (blasts ≤ 5%) within 2 induction cycles of blinatumomab treatment will undergo the safety follow-up visit and will be followed by telephone contacts in the long-term follow-up phase of the study.
- Subjects who go on to receive allogeneic hematopoietic stem cell transplant (alloHSCT) or begin other treatment for ALL at any time following the first treatment cycle will undergo the safety follow-up visit and will be followed by telephone contacts in the long-term follow-up phase of the study.

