#### **10.7.5.2 Analysis of Study Drug Exposure**

Data on study drug administration will be listed as recorded in a CRF (including information on dose changes) together with the calculated variables as defined above.

The duration of infusion [days] and the cumulative dose [ $\mu\text{g}$ ] will be tabulated for each cycle and the whole infusion for the SAF.

The relative treatment duration and the percent of the intended dose will be tabulated for each cycle and across cycles for the SAF

The number and percentage of subjects receiving distinct numbers of complete or incomplete cycles of blinatumomab will be summarized.

The number of cycles (complete and incomplete together) received will also be summarized by mean, standard deviation, minimum, median and maximum for each analysis set.

Reason for treatment interruptions (including due to adverse event) as documented during each treatment cycle will be tabulated for each dose level and cycle for all analysis sets by display of display of number and percentage of patients with each reason for interruption.

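### The across-cycles percent of intended dose may use a two-cycle denominator for subjects with two or fewer cycles but a cycles-started denominator for consolidation subjects, so one complete cycle with no missed dose can score about 45%

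*SAP*

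**What the plan says.** SAP 10.7.5.1 first defines absolute cumulative dose and then the percent of intended dose. The rule for the shorter courses is permissive: "For patients who receive two or fewer cycles, this may be calculated using the absolute cumulative dose received". The denominator in that rule is fixed at two cycles, since the amount is to be "divided by the planned cumulative dose patients should have received through two cycles". The planned amount is on a 56-day basis when no cycle was restarted ("then the planned cumulative dose will be based on 56 days for the first two cycles"). If cycle 1 or 2 was restarted, "then the planned cumulative dose for the first two cycles will be based on three times 28 days". Nothing adjusts the denominator when cycle 2 was never begun.

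For subjects who received consolidation, the rule is mandatory and different: the complete cumulative dose is "divided by the intended cumulative dose of all cycles that were started to compute the percent of the intended dose".

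SAP 10.7.5.2 says that "the percent of the intended dose will be tabulated for each cycle and across cycles", and SAP 10.7.5 summarises exposure by dose cohort and overall. Neither section says that the two versions are shown apart.

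Protocol 3.1 describes induction as "Up to two induction cycles of blinatumomab". The same section expects that some subjects will move to transplant or other leukemia treatment after the first cycle. Protocol 6.6 lists reasons for stopping that can apply after one cycle, among them progression and a switch to other therapy.

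**The concern.** A percent of intended dose is normally read as dose delivery: how much was lost to interruptions, reductions and mid-cycle withdrawals. Under the two-cycle denominator, a second cycle that was never started counts as lost dose, even where the protocol permitted or required the stop. Under the consolidation denominator, an unstarted cycle counts for nothing.

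Both kinds of subject appear to enter one across-cycles line. Consolidation is open only to subjects with a marrow response within two induction cycles (Protocol 3.1), so the choice of denominator is tied to outcome. The ordering of subjects can also reverse. One clean cycle would score about 45%, while a consolidation subject who received exactly half the intended dose of every started cycle would score 50%. Dose cohorts or study parts with different shares of one-cycle subjects could differ on this line without any difference in interruptions or reductions.

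**Working it through.** **Inputs**
- Cycle 1 is 7 days at the lower level and then 21 days at the higher level of a 28-day infusion; later cycles are 28 days at the higher level (Protocol 6.2.1).
- The adult regimen in the expansion cohort, given there as the Phase 2 dose, is 9-28 µg/day; the pediatric expansion regimen is 5-15 µg/m²/day (Protocol 6.2.2.3.1 and 6.2.2.3.2). The other regimens are in Protocol Tables 2 and 3.
- The denominators are those of SAP 10.7.5.1.

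**The SAP's own figures.** It prints no percent value, only the planned infusion basis. With no restart, 2 × 28 = 56 days. With one restart, 3 × 28 = 84 days. Both agree with the text.

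**One complete cycle, nothing missed, then a permitted stop**
- Cycle 1 dose = 7 × low + 21 × high; cycle 2 dose = 28 × high.
- Two-cycle rule: cycle 1 / (cycle 1 + cycle 2). Cycles-started rule: cycle 1 / cycle 1.
- Adult 9-28: cycle 1 = 7 × 9 + 21 × 28 = 651 µg; cycle 2 = 28 × 28 = 784 µg. 651/1435 = 45.4%, against 651/651 = 100%.
- Pediatric 5-15: cycle 1 = 7 × 5 + 21 × 15 = 350 µg/m²; cycle 2 = 28 × 15 = 420 µg/m². 350/770 = 45.5%, against 350/350 = 100%.

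| Cohort | Cycle 1 | Cycles 1 + 2 | Two-cycle rule |
|---|---|---|---|
| 1A (9-28) | 651 | 1435 | 45.4% |
| 1B (9-24) | 567 | 1239 | 45.8% |
| 1C (6-28) | 630 | 1414 | 44.6% |
| 1D (6-24) | 546 | 1218 | 44.8% |
| P1 (5-15) | 350 | 770 | 45.5% |
| P2 (5-10) | 245 | 525 | 46.7% |
| P3 (3.75-15) | 341.25 | 761.25 | 44.8% |
| P4 (3.75-10) | 236.25 | 516.25 | 45.8% |

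Dose units are µg for adults and µg/m² for pediatric subjects. Counting the day 8 to day 29 block as 22 days, and cycle 2 as 29, moves the adult 9-28 value only to 679/1491 = 45.5%. On infusion days alone the ratio would be 28/56 = 50%; the lower-dose first week brings it down to 45%.

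**Where the two rules agree.** Once cycle 2 has been started, both denominators are the planned dose of cycles 1 and 2. An adult who stops on day 1 of cycle 2 scores (651 + 28)/1435 = 47.3% either way. The difference is therefore confined to subjects who never start cycle 2.

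**What the cycles-started rule does to mid-cycle stopping.** An adult who completes two cycles and stops after day 1 of cycle 3 scores (651 + 784 + 28)/2219 = 65.9%. Stopping halfway through cycle 3 gives (1435 + 14 × 28)/2219 = 82.3%. A subject who completes three cycles and stops scores 100%.

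**The case against.** The strongest reply has four parts.

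1. **The two-cycle rule is an option.** The SAP says *may*, so the 45% appears only if the option is taken. This stands, and the conclusion is conditional on it. It also leaves the denominator open until the data have been seen, which is a reason to settle it.

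2. **Other planned output shows what happened.** SAP 10.7.5.2 also tabulates the percent by cycle, where this subject should show 100% for cycle 1. It adds infusion duration and cumulative dose by cycle, numbers of complete and incomplete cycles, and reasons for interruption, with individual listings. This stands. A reader might infer that the exposure tables as a whole cannot be used to judge tolerability; the documents do not support that. The defect is in the across-cycles line.

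3. **Two cycles is a sensible yardstick.** The primary endpoint and the marrow-response criterion both run over two cycles, so delivery against a full induction course is a meaningful quantity. That is fair as a separate measure. It does not rescue the definition, because the SAP does not label it so and drops it for consolidation subjects, who also had an induction course.

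4. **Changing the rule does not remove every deficit from stopping.** Mid-cycle stops still lower the score, as shown above, and a subject with one clean cycle would score 100% although induction was not completed. This stands as a cost of the change. The penalty would at least follow one rule for everyone.

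It is also tempting to project the size from the earlier pediatric study MT103-205, where Protocol 2.1.2 reports 19 of 39 subjects (49%) as having started and completed one cycle, and to infer that about half the subjects here would score 45% or less with no missed dose. The text does not support this. It does not say how many of the 19 began a second cycle, and it describes a heavily pretreated pediatric group. Under the 9-28 and 5-15 regimens, a subject with no missed dose who completes cycle 1 cannot score below 45.4% or 45.5%.

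**Conclusion.** The point holds as a minor defect of definition. One variable has two denominators, one optional and one mandatory. If the option is used, a subject who completes cycle 1 without a missed dose and permissibly stops scores 45.4% (adult 9-28) or 45.5% (pediatric 5-15) across cycles, and 44.6% to 46.7% over all eight cohort regimens, against 100% under the rule used for consolidation subjects.

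This assumes a 28-day planned infusion per cycle, no restart, and a single across-cycles summary for both groups. The last is the natural reading of SAP 10.7.5 and 10.7.5.2 but is not stated outright. The number of subjects affected cannot be estimated from the documents.

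The per-cycle rows are not affected, and no hypothesis test or stopping rule uses the variable. A reader might link it to the 85% dose threshold in Protocol 3.4. The documents do not make that link, and that threshold concerns subjects who leave before the DLT evaluation period ends.

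**What to change.** In SAP 10.7.5.1, define percent of intended dose for every subject as cumulative dose received divided by the intended dose of the cycles that subject started. Leave the counting of restarted cycles as it is, and replace *may be* with *will be*. Keep the number of cycles as a separate summary, as SAP 10.7.5.2 already plans.

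If delivery against the full two-cycle induction course is also of interest, report it as a second measure with its own label, computed for all subjects including those who go on to consolidation.

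The cost is a few lines of SAP text and one change to a derived variable, with no new data. The downside is that incomplete induction must be read from the cycle counts, and that stopping mid-cycle still lowers the score. A table footnote should say both.

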#### **10.7.5.2 Analysis of Study Drug Exposure**

Data on study drug administration will be listed as recorded in a CRF (including information on dose changes) together with the calculated variables as defined above.

The duration of infusion [days] and the cumulative dose [ $\mu\text{g}$ ] will be tabulated for each cycle and the whole infusion for the SAF.

The relative treatment duration and the percent of the intended dose will be tabulated for each cycle and across cycles for the SAF

The number and percentage of subjects receiving distinct numbers of complete or incomplete cycles of blinatumomab will be summarized.

The number of cycles (complete and incomplete together) received will also be summarized by mean, standard deviation, minimum, median and maximum for each analysis set.

Reason for treatment interruptions (including due to adverse event) as documented during each treatment cycle will be tabulated for each dose level and cycle for all analysis sets by display of display of number and percentage of patients with each reason for interruption.

#### **10.7.6 Exposure to Concomitant Medication**

The number and proportion of subjects receiving concomitant medications from study day 1 through safety follow-up will be summarized by preferred term as coded by the World Health Organization Drug (WHODRUG) dictionary in the SAF. In addition, the

number and proportion of subjects receiving anti-cancer therapies during long term follow-up will be summarized by WHODRUG preferred term for the SAF.

**Table 6. Definition of Different Types of Medication**

| Type of medication                         | Definition  |
|--|---|
| Prior medication                           | Start and stop before first blinatumomab infusion   |
| Concomitant medication                     | Start <=end of induction phase visit and stopped after first blinatumomab infusion or start during re-treatment |
| Medication started during follow-up period | Start day after end of induction phase visit, but not during re-treatment                                       |

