## 6.11 Excluded Treatments and/or Procedures During Study Period

The following medications are not permitted during a subject's participation during treatment phase (including the induction and consolidation phases of treatment) of this study:

- Tyrosine kinase inhibitor therapy (eg, imatinib, dasatinib, niolotinib, bosutinib, and ponatinib) are not permitted during treatment with blinatumomab
- Any anti-tumor therapy other than the blinatumomab:
  - Cytotoxic and/or cytostatic drugs
  - Radiation therapy
  - Immunotherapy
- Chronic systemic (> 7 days) high-dose corticosteroid therapy (dexamethasone > 24 mg/day or equivalent)
- Any other immunosuppressive therapies (except for transient use of corticosteroids)
- Any other investigational agent

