## 3. Study Overview

### 3.1 Study Design

This is an open-label **combined** two-part multi-center clinical study to evaluate the efficacy, safety, and tolerability of blinatumomab in adult and pediatric Japanese subjects with R/R B-precursor ALL. The Phase 1b part will investigate the safety, efficacy, PK, and PD of blinatumomab to determine the MTD in adult and pediatric Japanese subjects respectively with R/R B-precursor ALL. In adult subjects, the Phase 2 part will assess the safety and efficacy of the recommended dose level of blinatumomab identified in the Phase 1b portion of the study in the adult study population. No phase 2 part is planned for the pediatric population in this study.

The study design for Phase 1b, Phase 2 **and Expansion** parts include:

- A 2-week Screening and Pre-Phase Period  
The pre-phase period within the screening period is permitted for the administration of dexamethasone to reduce tumor burden and the incidence of tumor lysis syndrome.
- Induction Phase  
Up to two induction cycles of blinatumomab. A single cycle of blinatumomab is defined as 6 weeks in duration, which includes 4 weeks of continuous intravenous infusion (CIVI) of blinatumomab followed by a 2-week treatment-free interval.
- Consolidation Phase  
Subjects who achieve a bone marrow response (blasts  $\leq 5\%$ ) within 2 induction cycles of treatment may continue to receive additional consolidation cycles of blinatumomab (up to a maximum of 5 total induction and consolidation cycles, or disease progression, intolerable adverse event or withdrawal of consent) under the same schedule as outlined in the induction treatment phase above.

- A safety follow-up visit is required 30 ( $\pm$  3) days after last dose of blinatumomab. Following the safety follow-up visit, subjects will be followed at 3, 6, 9, 12, 18, and 24 months ( $\pm$  2 weeks) after treatment start for disease **and survival status**. Subjects will return to the clinic for assessments until relapse, with the following exceptions:
  - Subjects who fail to achieve a bone marrow response (blasts  $\leq$  5%) within 2 induction cycles of blinatumomab treatment will undergo the safety follow-up visit and will be followed by telephone contacts in the long-term follow-up phase of the study.

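### SAP Table 6 closes the concomitant-medication window at the end of induction, contradicting the Section 10.7.6 text, which runs to safety follow-up

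*SAP*

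**What the plan says.** SAP Section 10.7.6 sets the window in its text: the number and proportion of subjects "receiving concomitant medications from study day 1 through safety follow-up will be summarized", by coded preferred term. A second summary in that section covers anti-cancer drugs given in long-term follow-up.

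SAP Table 6, immediately below, is the only place where the SAP defines the medication categories:

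- Prior: begun and ended before the first blinatumomab infusion.
- Concomitant: "Start <=end of induction phase visit and stopped after first blinatumomab infusion or start during re-treatment".
- Started during follow-up: "Start day after end of induction phase visit, but not during re-treatment".

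On the design, SAP Section 3.1 provides "Up to two induction cycles of blinatumomab". Subjects with a marrow response "may continue to receive additional consolidation cycles of blinatumomab", and the cap is "up to a maximum of 5 total induction and consolidation cycles". The safety follow-up visit comes 30 (± 3) days after the last dose, so it falls after any consolidation. Protocol Section 6.8 collects relevant concomitant therapy from consent through safety follow-up.

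**The concern.** The text and the table beneath it give different end points for the same category. The text runs to safety follow-up. The table stops at the end of induction and reopens only for a phase that this trial does not have. A programmer who derives the category flag from Table 6 would label a drug first started in cycle 3, 4 or 5 as follow-up medication while the subject is on blinatumomab. Unless it were an anti-cancer drug used in long-term follow-up, it would then appear in neither of the two summaries planned in Section 10.7.6.

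The mismatch shows most clearly against the safety analysis. SAP Section 6 counts an adverse event as treatment-emergent if it starts between the first infusion and 30 days after the last. Under Table 6, an infection in cycle 4 would be an on-treatment event, and an antibiotic first used to treat it would be follow-up medication. What is at stake is the coherence and completeness of a descriptive table in the subjects with the longest exposure.

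**Working it through.** The plan states no figure to reproduce. The check compares passages and then does simple cycle arithmetic.

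**1. Do the anchors in SAP Table 6 exist?**

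- *End-of-induction visit.* The schedules of assessments (Protocol Tables 6 and 7) list screening, days within a cycle, the safety follow-up visit and, for Phase 1b/2, long-term follow-up. They contain no visit by that name.
- *Re-treatment.* The phases in Protocol Section 3.1 and SAP Section 3.1 are screening/pre-phase, induction, consolidation, safety follow-up and, for Phase 1b/2 only, long-term follow-up. The nearest idea is a cycle re-started after an interruption (SAP Section 10.7.5.1; cycle 1.1 in Protocol Sections 6.5.1.1 and 6.5.1.2). That is not a separate phase.
- *Consolidation.* SAP Table 6 does not mention it.

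**2. How much treatment lies outside the Table 6 window?**

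Inputs: a cycle is 42 days with 28 infusion days; the maximum is 5 cycles; Protocol Section 3.5.1 assumes 2 induction and 3 consolidation cycles; safety follow-up is 30 days after the last dose. Assumptions: no interruptions or prolonged intervals, and, because the visit is undefined, induction ends on the last day of cycle 2.

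- End of induction: 2 × 42 = day 84.
- Last dose: 4 × 42 + 28 = day 196. Safety follow-up: 196 + 30 = day 226.
- Infusion days outside: 3 × 28 = 84 of 5 × 28 = 140, or 60%.
- Share of the Section 10.7.6 window outside: (226 − 84)/226 = 142/226, or 63%.

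**3. Range under other assumptions**

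- If the visit is taken as day 29 of cycle 2 (42 + 29 = day 71), the infusion share stays at 60% and the window share becomes (226 − 71)/226 = 155/226, or 69%.
- If induction ends after one cycle and the cap allows four more, 4 × 28 = 112 of 140 infusion days (80%) and (226 − 42)/226 = 184/226 (81%) lie outside.
- For a subject with two induction cycles and no consolidation, the last dose is 42 + 28 = day 70 and safety follow-up is day 100. Medications started in the last 100 − 84 = 16 days (or 100 − 71 = 29 days under the earlier visit date) are outside.

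**4. Which medications does this change?**

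The output counts subjects by preferred term. A drug started by the end of induction and stopped after the first infusion meets Table 6 and is counted, whether or not it is given again later. Only a preferred term that a subject first uses after induction is lost. The percentages above are therefore shares of time at risk of misclassification. They do not estimate how many medications or subjects are misclassified.

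**The case against.** The strongest reply is that Section 10.7.6 alone says what will be tabulated, and its window already covers consolidation. The SAP change log records that this summary language was updated in version 2.0, and it agrees with the collection window in Protocol Section 6.8. No planned summary uses the Table 6 follow-up category. On this view Table 6 is wording that was not brought into line, and the reported table would be right. This stands in part: if programming follows the text, nothing is lost. But the SAP gives no order of precedence, and Table 6 is its only stated definition of the category. Reading re-treatment as consolidation would also remove the conflict, but nothing in the documents supports that reading.

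Several stronger readings are tempting and are not supported:

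- *That premedication and intrathecal prophylaxis in consolidation would go uncounted.* Adult dexamethasone precedes every cycle, pediatric premedication precedes cycle 1, and intrathecal prophylaxis is due before treatment and after each cycle (Protocol Sections 6.3.2 and 6.4). Subjects reaching cycle 3 are normally counted for these already.
- *That prophylaxis in consolidation would be mistaken for later anti-cancer therapy.* That summary is limited to long-term follow-up, which begins after the safety follow-up visit and does not exist in the expansion cohort.
- *That prohibited drugs would be hidden.* Their use is a reason for discontinuation recorded in the eCRF (Protocol Section 6.6), and important deviations are listed (SAP Section 10.3).
- *That the number affected can be read from the 40% response assumption, 0.40 × 21 = 8.4.* Section 3.1 of both documents sets entry to consolidation by marrow blasts of 5% or less. That is not CR/CRh*, even though the footnote to Protocol Table 2 uses CR/CRh*. Responders may also leave for transplant.

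**Conclusion.** The contradiction is real and the Table 6 rule is wrong for this design: it rests on a visit and a phase that the trial does not define, and it leaves out an on-drug phase. The consequence is conditional. If Table 6 governs the derivation, preferred terms first used in consolidation, or between the end of induction and the safety follow-up visit, are left out of the concomitant summary. For a subject completing the protocol's assumed five cycles, that covers 84 of 140 infusion days. How many subjects this touches cannot be derived from the documents; five cycles is the maximum, and in the pediatric study described in Protocol Section 2.1.2 only 2 of 39 subjects (5%) are listed with three cycles.

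The effect is confined to descriptive concomitant-medication summaries. The primary endpoint, error rates, sample size and DLT decisions are untouched. This is a minor point that is worth correcting because the stated rule is wrong and the correction is cheap.

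**What to change.** Rewrite SAP Table 6 to match the Section 10.7.6 text and the collection window in Protocol Section 6.8:

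- *Prior:* unchanged.
- *Concomitant:* taken at any time from the first blinatumomab infusion through the safety follow-up visit, across induction and consolidation, whatever the start date.
- *Started during follow-up:* started after the safety follow-up visit.
- Delete both re-treatment clauses.

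The cost is one table in the SAP and one derivation in programming. The data are already collected through safety follow-up, so neither the eCRF nor study conduct changes. Expansion subjects finish at the safety follow-up visit, so under the new wording none of their on-study medication would be called follow-up.
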